#### 7.2.2 Per Protocol Population

- *All subjects who adhere to the major criteria in the protocol with a  $\geq 90\%$  compliance*
- *If  $\geq 90\%$  of participants have full compliance, this analysis will not be performed*

### 7.3 Covariates and Subgroups

#### Protocol 1

Protocol 1 covariates included in analyses in section 9.1 include age, sex, body mass index,

pre-intervention 24 hour ambulatory systolic and diastolic blood pressure, and average of three systolic and diastolic blood pressure readings prior to the first Heat Therapy or Exercise Training session.

#### Protocol 2

Protocol 2 covariates/potential confounders that will be characterized for their relationship with each other and Protocol 1 and 2 outcomes as described in section 9.1 include are listed in **Table 5**.

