consent process will be completed for Protocol 1. We will also assess medical history, BMI, fasting glucose, hemoglobin A1c, and lipid profile to verify eligibility. If the subject is interested in participating in Protocol 2, the informed consent process for

**PRE-TESTS:** Before and after the **INTERVENTION**, we will conduct high-resolution phenotyping of subjects which will include: lab-based hemodynamic tests of vascular function; blood-based biomarkers related to cardiovascular health; 24-h urine collection; 24-h food/beverage log; 24-h ambulatory blood pressure recording; VO2peak fitness test. These are detailed below *Specific Experimental Approaches*. **ASSIGN:** Subjects will be randomized to either the heat therapy group or exercise training group, then undergo 30 sessions of the

specific intervention at a rate of 3-4 per week over an 8 to 10-week period. Randomization will be stratified by age and sex to ensure equal numbers within each stratum. Further stratification, for example by BMI or initial blood pressure, would be difficult given the small sample size. (More details of the randomization process are under *Randomization*). After the first 15 sessions, subjects will be re-tested for hemodynamic and biomarker adaptations to the intervention (INTERIM-TEST). After 30 sessions, subjects will undergo final POST-TESTS.

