## 5.3 Randomization and Blinding

**Randomization.** As indicated above, subjects will be randomized to either the heat therapy group or exercise training group. While subjects will not be blind to their treatment group, preliminary analysis of data and data entry will be by a blinded researcher (i.e., this will be a partially blind/observer-blind trial). The randomization and blinding process will be coordinated by [name] (a biostatistician at OHSU who is supporting this project). In brief, the Research Coordinator will enter age, sex, and subject ID number into a web-enabled randomization database via REDCap and receive the randomized group assignment. As indicated above, randomization will be stratified by age and sex to ensure equal numbers within each stratum. Further stratification, for example by BMI or initial blood pressure, would be difficult given the small sample size.

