## 9 Efficacy Analyses

For primary analyses for Protocol 1 Aims 1, primary outcomes will be compared between groups (heat therapy vs exercise training) over time (within subject repeated measurements) using two-way repeated measures mixed model including an interaction between intervention group and timepoint with pre-defined contrasts. For Specific Aim 1, to test the hypothesis that heat therapy improves blood pressure (both in clinic and 24H ambulatory) better than dynamic aerobic exercise, the null hypothesis will be that the interaction between group and timepoint is equal to 0. For Aim 2, to determine whether heat therapy will improve biomarkers of arterial health (arterial stiffness & biomarkers of systemic

inflammation and oxidative stress) and compare responses to exercise training, the null hypothesis will be that the interaction between intervention group and timepoint is equal to 0. For Aims 1 and 2 exploratory analyses, ANCOVA will be performed for primary and secondary outcomes, with pretest values entered as a covariate and treatment condition specified as a fixed factor. Demographic and physiological variables (age, sex, BMI) and pre-intervention blood pressure will be added one at a time to the ANCOVAs to test for an interaction on treatment effects. For Aim 3, we will use ANCOVA models to determine the predictive potential of acute post-exercise hypotension response for chronic changes in blood pressure, with pretest values entered as a covariate and systolic and diastolic blood pressure specified as a fixed factor. Analyses will be performed on the Intention to Treat population. Additionally, change from pre- to post-intervention in ambulatory and in clinic systolic and diastolic pressure will be correlated with change from pre- to post first intervention session supine systolic and diastolic blood pressure by Pearson correlation.

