For Protocol 2, where composite score cognitive function and brain biomarkers of ADRD risk outcomes were not collected at the interim timepoint, separate linear regressions will be performed for each outcome and predictor combination, where the post-intervention timepoint of the measure is the outcome, the pre-intervention measure of the outcome will be included as a covariate, and predictors will be intervention group in Aim 1 and 24H ambulatory systolic and diastolic blood pressure and arterial stiffness measures mean perfusion calibration in gray matter or white matter in Aim 2. Diagnostic plots and Cook's D of linear regressions will be assessed for influential outliers. If found and not improved through transformation, Robust regression using Huber weighting will be utilized instead.

Continuous outcomes will be transformed for normalcy prior to analysis. Methods used to check model assumptions will include checking for extreme outliers by visual inspection and Shapiro test and checking for homogeneity of variance by visual inspection and Levene's test. Full model results will be saved in an appendix or csv file, for possible use in planning future studies, meta-analysis and to enable replication of analysis.

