## 9.1 Exploratory Efficacy Analyses

In addition to Protocol 1 primary analyses, additional exploratory analysis will include analyses of covariance (ANCOVA) for each dependent variable of interest, in which pretest values will be entered as a covariate and treatment condition will be specified as a fixed factor in ANCOVA models. Demographic and physiological variables age, sex, and body mass index will be added one at a time to the ANCOVAs to test for an interaction on treatment effects using the following ANCOVA models with pre-intervention systolic or diastolic blood pressure (Pre SBP, Pre DBP) included as a continuous covariate. ANCOVA models based on the formula Interim or Post BP ~ Pre BP + <Interaction variable> + Intervention + <Interaction variable>\*Intervention and included the following terms in addition to Pre BP: Model 2, Pre BP\*Intervention; Model 3, Age + Age\*Intervention; Model 4, Sex + Sex\*Intervention interaction; Model 5, BMI + BMI\*Intervention interaction. SBP, DBP, age and body mass index (BMI) will all included in models as continuous variables with means estimated at selected values of interaction terms to illustrate how blood pressure measures did or did not vary by subgroup.

For Protocol 1 Aim 3, which is an exploratory aim, analyses of covariance (ANCOVA) models will be used to determine the predictive potential of acute responses for chronic changes in blood pressure. To test the association between acute decreases in blood pressure following an initial heat therapy session or exercise peak test and sustained reduction in resting blood pressures as measured by post-intervention ambulatory blood pressure, we will perform ANCOVA models with pre-session systolic or diastolic blood pressure (Pre-session SBP, Pre-session DBP) included as a continuous covariate. Pre-session BP is an average of three pre-session measurements and Post-session BP is lowest

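### The primary models leave out age and sex, the two stratification factors; adding them with timepoint interactions could gain a little precision

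*SAP*

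**What the plan says.** SAP 5.3 states that "randomization will be stratified by age and sex to ensure equal numbers within each stratum". SAP 5.1 and Protocol section C (the ASSIGN step and the Randomization paragraph) say the same. No document gives the age cut-point or a block size.

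For Protocol 1, SAP 9 specifies a "two-way repeated measures mixed model including an interaction between intervention group and timepoint", and for Aim 1 "the null hypothesis will be that the interaction between group and timepoint is equal to 0". Aim 2 has the same null. No covariate is listed for these models.

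SAP 7.3 links age and sex to the exploratory section: "Protocol 1 covariates included in analyses in section 9.1 include age, sex, body mass index". In SAP 9.1, "Demographic and physiological variables age, sex, and body mass index will be added one at a time to the ANCOVAs" as effect modifiers, so no listed model adjusts for both together. The exploratory part of SAP 9 does the same.

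For Protocol 2, SAP 9 says that "the pre-intervention measure of the outcome will be included as a covariate, and predictors will be intervention group in Aim 1". SAP Table 5, which lists the Protocol 2 covariates and potential confounders, contains neither age nor sex. The memory composite is built from age-corrected scores (SAP 4.2 and Table 4).

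No reason is given for leaving the stratification factors out of the primary models.

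**The concern.** Stratified allocation balances age and sex between arms. Where those factors predict the analysed response, the treatment estimate varies less from sample to sample than an unadjusted model assumes. That model leaves their contribution in the residual, so its standard error is somewhat large and its test somewhat conservative. Analysing by the factors used in randomisation recovers the precision that the design has bought.

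The stake is precision in a trial that plans for 40 completers. In Protocol 2 there is a second reason to adjust. That subset of up to 40 is formed by consent, handedness, MMSE score and MRI eligibility, so the balance created at randomisation need not carry over to it.

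**Working it through.** **The plan's own figures.** The plan gives no figure for how much age and sex explain. SAP 6 sizes the trial with an unadjusted two-sample t-test, a difference of 4.0 mmHg and an SD of 4.5 mmHg (4.0/4.5 = 0.89). With 20 completers per arm the standard error of the difference in change is √(2 × 4.5²/20) = 1.42 mmHg. Two-sided t-test power at d = 0.89 is then about 78%. (The stated enrolment of 50 does not reproduce at 90% power: 28 per arm, 56 completers, 56/0.8 = 70. That is a separate matter and does not depend on this point.)

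**Step 1: age and sex affect level only.** The contrast compares each person's post value with the same person's pre value, so anything constant over time cancels. Mixed-model fits to 60 simulated data sets (20 per arm, three timepoints, strata effects on level) were compared with and without age and sex main effects. The interaction estimate was the same (differences at rounding error) and its standard error was 1.424 in both. Only the group difference at a single timepoint became more precise (SE 3.07 to 2.72 under the assumed strata effect). Main effects alone therefore do nothing for the primary test.

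**Step 2: age and sex predict change.** Assumptions: random intercept per person, complete data, strata balanced across arms.
- Let σ² be the residual variance at one timepoint, so a change score has variance 2σ² within strata.
- Let strata add b² to the variance of the pre-to-post change. Then R² = b²/(b² + 2σ²), so b² = 2σ²R²/(1 − R²).
- The planned model pools residuals over three timepoints, with 2 within-person df per person.
- If the strata effect grows linearly (0, ½, 1), its within-person sum of squares is (¼ + 0 + ¼)b² = ½b². It adds ½b²/2 = b²/4 to the residual variance.
- If it is complete by the interim test (0, 1, 1), the sum is (4/9 + 1/9 + 1/9)b² = ⅔b². It adds b²/3.
- Standard-error ratio, unadjusted to correct: √(1 + k·R²/(1 − R²)), with k = ½ (linear) or ⅔ (early).

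| Assumed R² | R²/(1 − R²) | Ratio, linear | Ratio, early | Simulated excess |
|---|---|---|---|---|
| 5% | 0.0526 | √1.0263 = 1.013 | √1.0351 = 1.017 | 1.4–1.7% |
| 10% | 0.1111 | √1.0556 = 1.027 | √1.0741 = 1.036 | 2.8–3.9% |
| 20% | 0.2500 | √1.1250 = 1.061 | √1.1667 = 1.080 | 6.4–8.3% |

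The simulation fits the same model with 20 per arm. It runs slightly above the closed form because of finite degrees of freedom.

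**Step 3: type I error at R² = 20%.** 2Φ(−1.96 × 1.061) = 0.038 and 2Φ(−1.96 × 1.080) = 0.034. Simulation gives about 3.5–3.7%.

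**Step 4: power.** In a simulation with b = 2 mmHg and a linear profile, R² = 4/(4 + 20.25) = 16%. Adding strata-by-time terms lowered the SE from 1.49 to 1.42 and moved type I error from 0.037 to 0.048. With a true 4 mmHg difference, power rose from 76.7% to 79.1%.

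**Step 5: degrees of freedom.** With three timepoints and a two-level or continuous age term: age 1 + sex 1 + age-by-time 2 + sex-by-time 2 = 6.

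**The case against.** The case for leaving the plan alone is substantial.

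- **The primary contrast is within-person.** Stable age and sex effects cancel, and nothing in the documents shows that either factor predicts the change in blood pressure or pulse wave velocity. This stands, and it makes the size of the point conditional.
- **The sample-size basis is itself unadjusted.** Adjustment would be a gain over the planned power, not the repair of a shortfall caused by this omission. This stands.
- **Any error is in the safe direction.** Intervals are slightly wide, and SAP 7.5 describes the study as focused on learning and hypothesis generation. This stands and limits the weight of the point.
- **Protocol 2 is partly covered.** Each regression adjusts for the outcome's own pre value, and the memory scores are age-corrected. That leaves less to gain, but sex is unadjusted throughout and nothing says that the perfusion outcomes are age-corrected.

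A reader might infer that the primary standard errors must be wrong because the strata are ignored. Step 1 shows that this does not follow. A reader might also apply the change-score formula 1/√(1 − R²), giving 2.6%, 5.4% and 11.8% excess and type I error of 4.4%, 3.9% and 2.8%. That formula describes a comparison of a single change score. The planned model pools residual variance over three timepoints, and under a random intercept the excess is smaller.

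**Conclusion.** The point holds as a modest, conditional gain in precision. Age and sex define the strata, and no primary model in either protocol contains them. For the Aim 1 and Aim 2 tests the effect on the standard error is nil if they influence level only. It is about 1.5%, 3–4% and 6–8% if they explain 5%, 10% and 20% of change variance.

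Those shares are assumed, as are the random-intercept structure, exact balance within strata, complete data and 20 per arm. The SAP does not state the covariance structure, and with dropout the cancellation of level effects is only approximate. No size is offered for Protocol 2, because the documents give nothing from which to derive one.

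The documents do not support reading this as a source of bias or false positives: the error, where there is one, is conservative.

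**What to change.** - **SAP 7.3 and 9, Protocol 1:** add sex and age (the stratum as randomised, or continuous age) to the primary Aim 1 and Aim 2 models, each with its timepoint interaction. State which form of age is used and, if the stratum, its cut-point. The interactions are essential, because main effects alone leave the test unchanged.
- **SAP 9, Protocol 2:** add sex and age to the regressions. The gain from age is mainly for the perfusion outcomes.
- **SAP 13:** date the change and report the unadjusted result beside the adjusted one. The 04/11/2024 entry shows that some residual plots had already been examined. Both factors are fixed by the design, so adding them need not be data-driven, but readers should be able to see both results.
- **Alternatively,** state why the stratification factors are left out.

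The cost is a revision of SAP wording and four added terms (6 df) in each Protocol 1 primary model, more if the age stratum has over two levels. No new data are needed, because age and sex are entered in REDCap for randomisation.

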**Table 5. Protocol 2 Covariates and Potential Confounders**

	Cognitive	Brain biomarkers of ADRD risk
Covariates/ Potential Confounders	PSQI (sleep measure), MMSE (general cognitive assessment at baseline)	Hippocampal regions: Whole hippocampus, Left ERC, Right ERC, eTIV (for normalizing ERC measures) White matter hyperintensities (WMH): WMH volume, WMH Mean

#### 7.4 Missing Data

Descriptive statistics will be computed to understand the nature of the data collected, and to identify outliers and missingness patterns. We will follow procedures to minimize biases and limit power loss as a result of attrition, such as the use of mixed effect models that allow for missing data, and employ multiple data-imputation methods if greater than 10% of a predictor or covariate of interest is missing. Proposed analyses are designed to limit biases even when assumptions of data missing completely or missing at random do not hold. Participants with any study visits post-intervention will be included in analyses.

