## 6 Sample Size

**Projected effect sizes.** To estimate effect size for the primary outcome variables of systolic and diastolic blood pressures, we bracketed over several scenarios with varying pre- to post-intervention differences (i.e., with the fall in pressure following heat therapy being 4.0, 4.5, or 5.0 mmHg greater than following exercise training), and using a SD of 4.5 mmHg from our pilot work and published studies using similar interventions and approaches, which resulted in minimum hypothesized effect sizes of 0.89, 1.00, and 1.11 for Aim 1. For MSNA, we used a pre-intervention mean value of 39 $\pm$ 7 bursts/100beats based on our pilot data with 4 HTN subjects, and determined that a post-intervention mean value of 29 $\pm$ 7 b/100bts would represent a clinically significant change (of 10 b/100bts). Thus, for MSNA,  $d = 1.43$ .

Similarly, from our pilot work and our published studies using similar interventions and approaches, calculated effect sizes for  $\beta$ -stiffness  $d = 1.43$ , DAC  $d = 1.70$ , sympathetic baroreflex  $d = 1.33$ , FMD  $d = 2.55$ , carotid wall thickness  $d = 3.33$ , for Aim 2. Effect sizes for blood pressures were the lowest of our outcome variables; thus, powering for blood pressure will allow adequate power for numerous measurements giving us a global picture cardiovascular and autonomic health.

**Statistical power.** Our prospective power estimates based on a simpler model (two-sample RCT design, modeled as a two-sample t-test), to detect a minimum hypothesized effect size of 0.89 (which is smallest effect size of interest across outcome variables; power 90%;  $\alpha=0.05$ ), indicate the need to enroll 50 subjects (50:50 ratio of study groups; sample size assumes 20% dropout for the per-protocol analysis).

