### 7.2 Analysis Populations

Intention-to-Treat will be the primary analysis approach. However, as one goal is to compare outcomes when subjects maintain compliance with heat therapy and exercise training, we will also employ per-protocol analysis as a secondary approach, including subjects with  $\geq 90\%$  compliance. As an exploratory step, we will conduct analyses of variance to compare characteristics of dropouts vs. completers, as this may inform future endeavors.

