#### 7.2.1 Intention to Treat or Modified Intention to Treat

- *All participants who received any intervention and who participated in at least one post-baseline assessment*

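### SAP 7.4 says bias is limited even when data are not missing at random, but no planned analysis of the Aim 1 blood pressure outcomes relaxes that assumption

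*SAP*

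**What the plan says.** SAP 7.4 claims of the planned analyses: "Proposed analyses are designed to limit biases even when assumptions of data missing completely or missing at random do not hold". It names two devices. The first is a modelling choice, "such as the use of mixed effect models that allow for missing data". The second is to "employ multiple data-imputation methods if greater than 10% of a predictor or covariate of interest is missing".

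The rest of the plan fits around these:

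- **Primary model (SAP 9):** the Aim 1 outcomes are compared between groups over time "using two-way repeated measures mixed model including an interaction between intervention group and timepoint with pre-defined contrasts". The outcomes are clinic and 24-hour ambulatory systolic and diastolic pressure (SAP Table 1), each measured before, midway through and after the intervention.
- **Analysis set (SAP 7.2.1):** "All participants who received any intervention and who participated in at least one post-baseline assessment".
- **Other steps (SAP 7.2):** "we will also employ per-protocol analysis as a secondary approach", restricted to at least 90% compliance. As an exploratory step, "we will conduct analyses of variance to compare characteristics of dropouts vs. completers, as this may inform future endeavors".
- **Expected loss (SAP 6):** "sample size assumes 20% dropout for the per-protocol analysis". The Protocol's power section expresses this as 50 enrolled so that 40 complete.

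The Protocol text contains no missing-data method of its own.

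**The concern.** A likelihood mixed model recovers the treatment effect when the chance of being missing depends only on what has been observed. Standard multiple imputation rests on the same condition. Under this plan imputation would not in any case be applied to a missing blood pressure outcome. So the claim in SAP 7.4 about what happens when MAR fails has no analysis behind it that examines such a failure.

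Informative dropout is plausible in this trial. Participants know their group, the two interventions make different demands, and a fifth of the sample is expected to be lost. The Protocol (Subject Rights and Withdrawal) allows an investigator to stop a participant for low session compliance, for discomfort, or for signs of stress that include very high blood pressure. That last route can link discontinuation to the outcome through readings that are not among the modelled pre, interim and post values.

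At stake is what the trial can say about robustness. As SAP 7.4 is worded, a report could describe the primary result as protected against informative dropout when that was never tested.

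**Working it through.** **1. Does any planned analysis relax MAR for the Aim 1 outcomes?**

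| Planned step | Where | Relaxes MAR for missing BP outcomes? |
|---|---|---|
| Mixed model, group by timepoint | SAP 9 | No; valid under MAR |
| Multiple imputation above 10% missing | SAP 7.4 | No; predictors and covariates only, and no departure from MAR specified |
| Review of missingness patterns | SAP 7.4 | No; descriptive |
| Per-protocol analysis | SAP 7.2 | No; selects on compliance after randomisation |
| Dropouts versus completers | SAP 7.2 | No; compares characteristics, does not re-estimate the effect |
| Exploratory ANCOVA | SAP 9, 9.1 | No; no method for missing outcomes stated |
| Huber regression | SAP 9 (Protocol 2) | No; addresses outliers, for other outcomes |

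**2. What the primary model does and does not handle.** A large-sample simulation used a true difference of -4.0 mmHg, SD 4.5, about 21% dropout in the heat arm and random 20% dropout in the exercise arm. The assumed dropout slope was log-odds 1 per SD.

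- Dropout driven by the observed interim change (MAR): estimate -4.00, no bias.
- Dropout driven by the unobserved final change (not MAR): estimate -4.44, which is 0.44/4.0 = 11% too favourable to heat.

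A second calculation compared the MAR likelihood estimate with completers only. It assumed 20% dropout in one arm driven by the unobserved post value, with the same slope and SD. Completer bias was 0.78 mmHg.

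| Interim-post correlation | 0.3 | 0.5 | 0.7 | 0.8 |
|---|---|---|---|---|
| MAR likelihood bias (mmHg) | 0.72 | 0.60 | 0.42 | 0.30 |

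The interim readings reduce the bias but do not remove it.

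**3. Size under assumed departures.** Inputs from the documents (SAP 6 and the Protocol's power section) are a smallest target difference of 4.0 mmHg, SD 4.5 mmHg, 50 enrolled in two equal groups and 20% dropout. The departure delta is an assumption, since neither document gives one.

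The 20% is trial-wide: 0.20 x 50 = 10 people. Spread evenly, that is 5 of 25 per arm (f = 20%). All in one arm, it is 10 of 25 (f = 40%).

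With a departure in one arm only, bias = f x delta:

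| | delta = 2 | delta = 4 | delta = 6 |
|---|---|---|---|
| f = 20% | 0.4 | 0.8 | 1.2 mmHg |
| f = 40% | 0.8 | 1.6 | 2.4 mmHg |

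As a share of 4.0 mmHg, this is 10% to 30% at f = 20% and 20% to 60% at f = 40%. With departures in both arms, net bias is f1 x delta1 - f2 x delta2, which is zero when the fractions and departures are equal.

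**4. Would a tipping-point analysis be informative?** Take an observed difference of 4.0 mmHg with 20 completers per arm and hold the standard error fixed.

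- SE = 4.5 x sqrt(2/20) = 1.423; t(38) = 2.024; lower 95% limit = 4.0 - 2.024 x 1.423 = 1.12 mmHg.
- Tipping delta at f = 20%: 1.12/0.20 = about 5.6 mmHg.
- Tipping delta at f = 40%, same SE: 1.12/0.40 = about 2.8 mmHg. With the completers this would actually leave (15 and 25), SE = 4.5 x sqrt(1/15 + 1/25) = 1.470, the lower limit is 1.02, and the tipping delta is 1.02/0.40 = about 2.6 mmHg.

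All of these lie inside a 0 to 6 mmHg range.

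**The case against.** The strongest reply is that SAP 7.4 promises only to limit bias, not to be valid when MAR fails. That stands. A reader might infer that the sentence is simply false and that the analysis has none of the property claimed. The documents do not support this: the primary model uses interim blood pressure, and step 2 shows it can cut the bias well below that of a completer analysis when interim and post values are closely correlated.

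A reader might also infer that all dropout from poor response goes unaddressed. That is too broad. Poor response already visible at the interim test is observed data, and dropout driven by it is handled under MAR. It would likewise be wrong to say that nothing else is planned, because SAP 7.2 sets out a per-protocol analysis and a dropout-versus-completer comparison. Neither, however, estimates the effect under a departure from MAR.

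Three further points have force:

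- The departures are assumptions, and 6 mmHg is 6/4.5 = 1.33 of the plan's SD.
- Different reasons for leaving in the two arms are plausible but not stated in the documents.
- SAP 7.5 describes the study as focused on learning and hypothesis generation, so a sensitivity analysis in so small a trial could be called optional. But SAP 7.4 makes a specific claim about departures from MAR, and supporting it is cheap.

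The phrase introducing the mixed model leaves the list of methods open, but no further method for missing outcomes appears in either document.

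**Conclusion.** The concern holds in this limited form: the plan claims some protection when MAR fails, yet includes no analysis that examines such a failure for the Aim 1 outcomes. The uncovered cases are dropout driven by unobserved final values and participants with no post-baseline assessment, whom SAP 7.2.1 leaves out. How many participants fall into either group is not known from the documents.

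The f x delta range in step 3 rests on a departure confined to one arm. Its upper half also requires all planned dropout to fall in that arm. Actual bias may be small, zero, or in either direction. The documents do not show that the trial's result is biased; they show that its robustness to informative dropout would not have been tested. The simulated biases depend on the assumed dropout slope and interim-post correlation.

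This should be changed, because it is inexpensive and determines what the report can claim about missing data.

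**What to change.** 1. Replace the sentence in SAP 7.4 with: *The primary mixed model assumes data are missing at random.*
2. Add a supportive delta-adjusted multiple-imputation (tipping-point) analysis of the post-intervention values of the four Aim 1 blood pressure outcomes. Shift the imputed values by 0 to 6 mmHg in each arm separately, include randomised participants with no post-baseline data, and report the shift at which the conclusion changes. If it does not change within the range, report that.
3. Date the change in the SAP's summary of changes. SAP 8.2 already refers to a deviation uncovered during analysis, so results may be known; if they are, label the analysis post hoc.

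The cost is SAP wording and a little programming, with no new data. The limitation is that with about five missing per arm the result rests on few imputed values, so it should support the primary analysis and not replace it.
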